## **ABBREVIATIONS AND DEFINITIONS OF TERMS**

Abbreviation	Definition
ANCOVA	Analysis of covariance
CI	Confidence interval
CIOMS	Council for International Organizations of Medical Sciences
CRF	Case report form
ECG	Electrocardiogram
EOT	End of treatment
GCP	Good clinical practice
GDPR	General Data Protection Regulation (European Union)
HIPAA	Health Insurance Portability and Accountability Act
ICF	Informed consent form
IFN	Interferon
IL	Interleukin
IMP	Investigational medicinal product
IRB	Institutional review board
NRS	Numeric rating scale
Ob(x)	Observation visit x
PPS	Per protocol set
Q2W	Every 2 weeks
SAE	Serious adverse event
SAF	Safety set
SUSAR	Suspected unexpected serious adverse reactions
TEAE	Treatment emergent adverse events
TNF	Tumor necrosis factor
V(x)	Visit x

#### **Definitions of Terms**

Term	Definition
Investigational medicinal product (IMP):	A pharmaceutical form of an active substance or placebo being tested or used as a reference in a clinical study.
Enrolled:	A subject is considered to be enrolled in a study as soon as he/she signed informed consent (i.e., at screening).
Measurement:	Recording the value of a variable, e.g., recording of blood pressure.
Procedure:	Specific test performed on the subject, e.g., sphygmomanometry after 10 minutes in supine position.
Assessment or evaluation:	Systematic judgment of the recorded variable, e.g., clinical relevance of abnormal blood pressure.
Variable:	A measurable attribute or event that have either qualitative or quantitative values which may be expected to vary over time and within or between subjects, e.g.: diastolic blood pressure at baseline (mmHg); diastolic blood pressure at Week 4 (mmHg)
Endpoint:	A variable that pertains to an objective of a study, e.g., mean change in diastolic blood pressure from baseline to Week 4 or percentage of responders at Week 4.
Baseline value:	The last measurement of a variable before the first dose of IMP.

#### **Rationale:**

IFX-1 is a monoclonal antibody (which specifically binds to the soluble human complement split product C5a) that is being developed for the treatment of various diseases in which complement activation plays a role.

Neutrophilic dermatoses are a spectrum of inflammatory disorders characterized by skin lesions resulting from a neutrophil-rich inflammatory infiltrate in the absence of infection. Pyoderma gangrenosum is associated with a neutrophilic leukocytosis, which is likely to be triggered by C5a. Pyoderma gangrenosum lesions have pronounced neutrophilic infiltration and the expression of interleukin (IL)-1 $\beta$ , IL-17, tumor necrosis factor (TNF)-alpha, and their receptors is significantly elevated, indicating an auto-inflammatory condition. C5a represents a promising target for blocking and modulating acute or chronic inflammation. Several animal models have demonstrated a positive impact of a blockade of the C5a/C5aR signaling axis on acute and chronic inflammatory diseases. A recent open label study deploying IFX-1 in 12 subjects suffering from hidradenitis suppurativa revealed early evidence of disease modifying activity of IFX-1 in this neutrophil driven skin disorder, with a sustained clinical response even after only 8 weeks of treatment. Given the neutrophil driven nature of pyoderma gangrenosum, the current study is designed to investigate whether IFX-1 could also be a treatment option for this autoimmune type dermatosis.

InflaRx	Clinical Study Protocol,
	Version 4.0 Including Amendment 02, 14 May 2020
IFX-1	IFX-1-P2.7

# **Objectives and Endpoints:**

Objectives	Endpoints
Primary	
• Explore the safety of IFX-1 for the treatment of subjects with pyoderma gangrenosum	• Occurrence, nature and intensity of treatment emergent adverse events (TEAEs), related TEAEs, serious TEAEs, and adverse events of special interest
Key Secondary	
• Explore the efficacy of IFX-1 for the treatment of pyoderma gangrenosum	
 
Responder rate defined as Physician's Global Assessment ≤3 of target ulcer at Visits V4, V6, V10, and V16 (End of Treatment [EOT])
 
Time to complete closure of pyoderma
 

	gangrenosum target ulcer (investigator assessment)
• Explore additional clinical outcome parameters in subjects with pyoderma gangrenosum under the treatment with IFX-1	• Percentage change in wound area and wound volume (wound healing) of target ulcer between Visits V1-V4, V1-V6, V6-V10; V10-V16, and V1-V16 (photographic assessment)
	• Rate of change per day in area of target ulcer (photographic assessment)
	• Number of subjects with a decrease in area of target ulcer of 50% or more at Visit V16 (EOT) compared to baseline (photographic assessment)
	• Number of subjects with a decrease in area of target ulcer of 100% at Visit V16 (EOT) compared to baseline (remission) (photographic assessment)
	• Degree of erythema and border elevation of the target ulcer compared to baseline at Visits V4, V6, V10, and V16 (EOT) (investigator assessment)
	• Mean change from baseline in pain assessed by Numeric Rating Scale (NRS) at Visits V4, V6, V10, and V16 (EOT)
	• Mean change from baseline in Dermatology Life Quality Index (DLQI) at Visits V4, V6, V10, and V16 (EOT)

InflaRx	Clinical Study Protocol,
	Version 4.0 Including Amendment 02, 14 May 2020
IFX-1	IFX-1-P2.7

#### Scientific exploratory parameters

The following will be collected at the time points given in the Schedule of Assessments (Section 2).

Blood for the analysis of:

•				

Fluid draining from the target ulcer, if available, for the analysis of:

• Immunology:

o		

• Bacteria using a bacterial culture and polymerase chain reaction

Biopsy from the target ulcer border tissue for immunostaining for:

Stool samples for the analysis of:

Absolute values and changes from the baseline value will be evaluated for the above parameters.

In addition, routine safety laboratory tests will be performed. Blood will also be analyzed for antineutrophil cytoplasmic antibody (ANCA) and antinuclear antibody (ANA) formation.

## **Overall Design:**

This is an open-label explorative study in subjects with pyoderma gangrenosum. Subjects will be examined according to the Schedule of Assessments (Section 2) at each visit. All subjects will receive IFX-1 (IMP). The IMP will be administered exclusively at site visits (Visit V1 to Visit V15). Examinations are defined in the Schedule of Assessments (Section 2). At the end of treatment with IMP, subjects should complete an End of Treatment (EOT;

InflaRx	Clinical Study Protocol,
	Version 4.0 Including Amendment 02, 14 May 2020
IFX-1	IFX-1-P2.7

gangrenosum at the discretion of the investigator. Subjects will be followed up for an additional after EOT for safety reason, with two observation visits (Visit Ob1 after 30 days and Visit Ob 2 after 60 days). Visit Ob2 is the final visit in the study.

#### Number of Subjects:

This is planned to be a multi-center study with about 18 subjects treated with IMP (IFX-1).

Subjects discontinuing treatment will not be replaced. It is expected that approximately 15 subjects will undergo at least months treatment.

#### **Treatment Groups and Duration:**

The estimated recruitment period is approximately 6 to 12 months.

If a subject discontinues the trial prematurely for any reason, they should have a termination visit (Visit V16 = EOT) and should be followed up at Visit Ob1 and Visit Ob2.

All subjects will receive IFX-1 at a maximum of 15 dosing visits.

There will be 3 dosing groups (Group 1, Group 2, and Group 3) of 6 subjects each. Each group of subjects is recruited sequentially. The next dose group will be initiated if the previous dose was considered safe and well tolerated. If dosing in Group 2 cannot be initiated, then a further 6 patients will be recruited in Group 1.

InflaRx	Clinical Study Protocol,
	Version 4.0 Including Amendment 02, 14 May 2020
IFX-1	IFX-1-P2.7

#### **Study Population Inclusion Criteria:**

#### Informed Consent

1. Capable of giving signed informed consent as described in Regulatory and Ethical Considerations (63), which includes compliance with the requirements and restrictions listed in the informed consent form and in this protocol, and approval for photographic documentation

#### Age

2. Subjects must be18 years or older, at the time of signing the informed consent

Sex

3. Male or female

#### Type of Subject and Disease Characteristics

- 4. Diagnosis of an ulcerative form of pyoderma gangrenosum confirmed by the investigator
- 5. In addition, the subject must fulfill at least 3 of the following 6 criteria at screening:

#### History of

- Pathergy (ulcer occurring at the sites of trauma)
- Personal history of inflammatory bowel disease or inflammatory arthritis
- History of papule, pustule or vesicle that rapidly ulcerated

Clinical examination (or photographic evidence) of

• Peripheral erythema, undermining border, and tenderness at site of ulceration

- Multiple ulcerations
- Cribriform or "wrinkled paper" scar(s) at sites of healed ulcers
- 6. Subject has a minimum of 1 evaluable ulcer ( $\geq 2 \text{ cm}^2$ ) at screening

#### **Study Population Exclusion Criteria:**

Subjects are excluded from the study if any of the following criteria apply:

#### Related to Presenting Medical Condition

- 1. Pyoderma gangrenosum target ulcer for more than 3 years before screening
- 2. Surgical wound debridement within the previous 2 weeks before screening

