#### Prior/Concomitant Therapy

- 10. Infection requiring suppressive anti-infective therapy (such as latent tuberculosis, pneumocystis, aspergillosis, cytomegalovirus, herpes simplex virus, herpes zoster and atypical mycobacteria)
- 11. Use of intravenous antibacterial, antiviral, anti-fungal, or anti-parasitic agents within 30 days before screening
- 12. Any drug treatment for pyoderma gangrenosum including corticosteroids (>10 mg prednisone or prednisone equivalent), intralesional steroids, cyclosporine A, biologicals and immunosuppressives (with the exception of antibiotics for wound superinfection) used within a time of 5 half-lives of the drug before screening (see 81)
- 13. Received live attenuated vaccine within the previous 3 months before screening
- 14. Major surgery planned during the time of foreseen study participation

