# 5.2 Study Sites, Study Subject, and Expected Duration

This study is planned to be a multi-center study with about 18 subjects treated with IMP (IFX-1).

The study start is defined as the date of the first visit of the first subject enrolled (signature of the informed consent form by the first subject), and the end of the study is defined as the date of the last visit of the last subject participating, as recorded in the Case Report Form (CRF).

The estimated recruitment period is approximately 6 to 12 months.

The study duration for an individual subject includes screening (14 days range 7 to 35 days), the treatment period (189 days  $\pm$ 5 days; the last day of dosing of IFX-1 is Day 169), and the observational follow up (60 days  $\pm$ 5 days).

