### 9.1.2 Start of IMP: Visit V1 (Day 1)

The following will be performed at Visit V1:

- Review all inclusion and exclusion criteria
- Record Dermatology Life Quality Index
- Record pain intensity using a numeric rating scale
- Document concomitant medications
- Record adverse events
- Record body weight
- Record vital signs
- Perform a physical examination
- Assess target ulcer (degree of erythema and border elevation)
- Take photograph of target ulcer for area and volume measurements. This photograph is the baseline for the recording of the Physician's Global Assessment at subsequent visits.
- Record a 12 lead ECG
- Take blood for
  - Immunology
  - Anti-drug antibody, antineutrophil cytoplasmic antibody, and antinuclear antibody
- Take a sample of the target ulcer fluid if wound is open and liquid is available
- Take a biopsy of the target ulcer
- Perform a urine pregnancy test for a woman of childbearing potential
- Take a stool sample for the measurement of calprotectin
- Use a standard dressing and compression therapy for the target ulcer

If the subject fulfills all of the inclusion criteria, does not meet any of the exclusion criteria, and written informed consent is available, the subject will be started on IMP.

- Assign subject to treatment
- Administer IMP
- Update recording of adverse events

Subjects enrolled into the study will be issued a subject card with relevant contact details, including emergency contact details.

If the subject meets an exclusion criterion or another reason for non-inclusion in the study is present after obtaining informed consent, the subject will not be enrolled into the study and will be deemed as screen failure.

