## 9.2.2 Medical History

Relevant medical (and surgical history), including date of diagnosis of pyoderma gangrenosum, in the investigator's opinion will be recorded in the CRF at screening. The medical history will be reviewed and updated on Day 1 to ensure that the subject remains qualified for the study.

InflaRx	Clinical Study Protocol,
	Version 4.0 Including Amendment 02, 14 May 2020
IFX-1	IFX-1-P2.7

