#### Physician's Global Assessment

The following scores will be used to rate overall efficacy (Foss 2008):

Severity score	Description
0	Completely clear: except for possible residual hyperpigmentation
1	Almost clear: very significant clearance (about 90%); however, patchy remnants of dusky erythema and/or very small ulceration
2	Marked improvement: significant improvement (about 75%); however, a small amount of disease remaining (i.e. remaining ulcers, although have decreased in size, minimal erythema and/or barely perceptible border elevation)
3	Moderate improvement: intermediate between slight and marked; representing about 50% improvement
4	Slight improvement: some improvement (about 25%); however, significant disease remaining (i.e. remaining ulcers with only minor decrease in size, erythema or border elevation)
5	No change from baseline
6	Worse

InflaRx	Clinical Study Protocol,
	Version 4.0 Including Amendment 02, 14 May 2020
IFX-1	IFX-1-P2.7

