## **10.3.2 Efficacy Analyses**

The efficacy of IFX-1 for the treatment of skin lesions due to pyoderma gangrenosum is one key secondary objective of this study. Further additional clinical outcome measures will also be investigated. The efficacy endpoints include:

- The responder rate based on the Physician's Global Assessment at Visits V4, V6, V10, and V16 (EOT). Response is defined as a Physician's Global Assessment of ≤3 at the target ulcer
- Time to complete closure of pyoderma gangrenosum target ulcer as assessed by the investigator
- Percentage change in wound area and volume assessed by measurement of photographs of the target ulcer between selected visits (i.e., change between Visits V1 and V4, V1 and V6, V6 and V10, V10 and V16, and V1 and V16)
- Rate of change calculated per day in the area of the target ulcer derived from the photographic measurements
- Number of subjects with a decrease in area of the target ulcer of 50% or more at Visit V16 compared to baseline derived from the photographic measurements
- Number of subjects with a decrease in area of the target ulcer of 100% at Visit V16 compared to baseline derived from the photographic measurements
- A wound healing assessment based on the investigators rating of the target ulcer's erythema and border elevation at Visits V4, V6, V10, and V16 (EOT)

Continuous variables, such as the target ulcer area and ulcer volume, will be analyzed by absolute values and changes from baseline, if applicable. Basic descriptive statistics (e.g., number of observations (n), mean, standard deviation, minimum, median, maximum, lower quartile, upper quartile) will be displayed by visit. All efficacy endpoints will be analyzed descriptively only. Therefore, p-values or confidence intervals resulting from possible statistical models or tests will be interpreted descriptively only. No statements concerning statistical significance are valid.

The number and percentage of subjects in each category will be displayed by visit for categorical or binary variables, such as the responder rate based on the Physician's Global Assessment or the number of subjects with remission.

The time to complete closure will be analyzed with Kaplan-Meier methods using the date of first IMP administration as reference time point. The date of complete closure represents the event date. Subjects who do not experience complete closure of the target ulcer will be censored at the date of their last assessment.

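### The debridement exclusion looks back from screening, but the efficacy baseline is V1, 7 to 35 days later, so at the planned 14-day interval it covers none of the last 14 pre-baseline days

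*Combined protocol and SAP*

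**What the plan says.** Exclusion 2 in the synopsis rules out "Surgical wound debridement within the previous 2 weeks before screening". It is the only mention of debridement in the text available. Section 5.2 says that each subject's time in the study "includes screening (14 days range 7 to 35 days"), followed by the treatment period, so the look-back ends one to five weeks before dosing.

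Efficacy is measured from V1:

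- Definitions of Terms gives the baseline value as "The last measurement of a variable before the first dose of IMP".
- Section 9.1.2 says of the V1 photograph: "This photograph is the baseline for the recording of the Physician's Global Assessment at subsequent visits".
- Section 10.3.2 compares area and volume as "change between Visits V1 and V4, V1 and V6, V6 and V10, V10 and V16, and V1 and V16". Three of these five comparisons start at V1.
- A PGA responder scores 3 or lower, and score 3 is described as "representing about 50% improvement" (section 9.3.1).
- Section 7.1.2 makes a PGA of 4 or more at Day 57 one condition for raising the dose in Groups 1 and 2.

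Other text that bears on the gap:

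- Section 9.1.2 repeats the eligibility review at V1. It also makes a subject a screen failure for reasons beyond the listed exclusions.
- Section 9.2.2 adds: "The medical history will be reviewed and updated on Day 1 to ensure that the subject remains qualified for the study".
- Section 7.2.2 refers wound care to Appendix 6, which lists dressings, compression and antiseptics.
- Section 7.2.3 lists what is prohibited from screening onward; debridement is not on it.
- Exclusion 14 concerns planned major surgery only.

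**The concern.** An exclusion for recent debridement protects whichever examination it is tied to. This one is tied to screening, while change is counted from V1. A subject debrided five days before V1 does not meet exclusion 2 as worded, and repeating the review at V1 does not alter that wording.

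Other pre-screening restrictions are carried forward. Exclusion 12 covers "Any drug treatment for pyoderma gangrenosum including corticosteroids (>10 mg prednisone or prednisone equivalent") and other agents, and section 7.2.3 continues that restriction from screening. The live-vaccine and other-study exclusions (13 and 15) also have counterparts there. Exclusion 2 has none. The pattern is not complete, since exclusion 11 has none either.

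The study has no control arm. If debridement enlarged an ulcer shortly before V1, closure of the enlarged part would be counted as improvement and could not be separated from drug effect. The outcomes open to this are the V1-anchored area and volume changes, the rate per day if it is taken from V1, the count with at least a 50% area decrease, and possibly the PGA with its Day 57 dosing rule. Complete closure, the 100% decrease, and the V6–V10 and V10–V16 changes are not altered arithmetically.

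**Working it through.** The plan states no coverage figure, so there is none to reproduce.

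**Coverage before baseline.** Inputs are the 14-day look-back (exclusion 2) and the screening-to-V1 interval S, planned at 14 days and allowed from 7 to 35 (section 5.2). The criterion covers the 14 days ending at screening. The days it shares with the 14 days before V1 number max(0, 14 − S).

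| S (days) | Days covered, of the last 14 | Days from screening to V1 not covered |
|---|---|---|
| 7 | 7 | 7 |
| 10 | 4 | 10 |
| 13 | 1 | 13 |
| 14 (planned) | 0 | 14 |
| 35 | 0 | 35 |

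Of the 29 allowed whole-day intervals (35 − 7 + 1), only the 7 from S = 7 to S = 13 give any coverage. Counting the screening day itself as covered adds one day (8 at S = 7, 1 at S = 14). If the ±2-day visit window could shorten S to 5, the best case would be 14 − 5 = 9, but the stated minimum of 7 argues against that reading.

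**Illustration of what a debridement could do to area.** The documents give no debridement margin. Assume a circular ulcer of area A, an even margin m of 1 to 2 mm removed before V1, complete healing of that margin, and no other effect on later area. With r = √(A/π), V1 area is inflated by x = ((r + m)/r)² − 1. If h is the decrease that would have been seen without the debridement, the recorded decrease is 1 − (1 − h)/(1 + x). Setting this to 0.50 gives h = (1 − x)/2.

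| A | m | x | h recorded as 50% |
|---|---|---|---|
| 2 cm² (entry minimum), r = 0.798 cm | 1 mm | 26.6% | 36.7% |
| 2 cm² | 2 mm | 56.4% | 21.8% |
| 6 cm² (size named in section 3.2.3), r = 1.382 cm | 1 mm | 15.0% | 42.5% |
| 6 cm² | 2 mm | 31.0% | 34.5% |

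Only a subject whose true decrease lies between h and 50% would be reclassified; at 6 cm² and 1 mm that band is 42.5% to 50%. One reclassified subject is 1/6 = 16.7 percentage points in a dosing group or 1/18 = 5.6 points overall. That is the granularity of the sample and holds for any misclassification.

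**The case against.** The case for leaving the criterion alone has several parts.

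- **Permitted care.** Appendix 6 is headed as the permitted wound care and omits debridement, which implies that it is not allowed. This stands as an implication, but it is not an eligibility rule, and section 7.2.2 also refers to standard of care.
- **The V1 gate.** Section 9.1.2 allows a subject to be turned away for reasons outside the listed criteria, and the history is updated that day. An investigator could stop a freshly debrided subject. This stands too, but it is discretionary and need not be applied alike across sites.
- **Pathergy.** The protocol lists it as a diagnostic feature and says that about a quarter of cases may follow trauma (section 3.2.2). Investigators have reason not to debride, and a debrided ulcer might worsen, which would act the other way.
- **Purpose.** The reason for exclusion 2 is not stated. It may protect the diagnosis and the size requirement, both set at screening. Even so, V1 is left uncovered.
- **Recording.** Section 7.2.1 already extends to procedures with dates, and photographs are taken at both visits. But section 3.2.2 says that these lesions can expand rapidly, so a jump in area alone would not identify a debridement.

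A reader might infer that debridement is expected at the wound-care sessions held two or three times a week. Nothing links those sessions to surgical debridement. A reader might also take the area illustration as an estimate of bias in the responder rate. It is not one: the margin is assumed, its full healing is the case most favourable to the concern, and the PGA also weighs erythema and border elevation, so area arithmetic does not carry over to it.

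**Conclusion.** The gap in the wording is real: at best 7 of the last 14 pre-baseline days are covered, and none at the planned interval or beyond. This rests only on the stated 7-to-35-day range and on V1 being the reference visit.

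The consequence is minor. The documents give no frequency of debridement, the direction of any distortion is uncertain, the efficacy endpoints are secondary and descriptive, and the primary safety endpoint is not touched. The one route beyond the descriptive tables is the Day 57 rule. If an enlarged baseline made the PGA look better, a dose increase might be withheld; if the ulcer worsened after debridement, one might be triggered.

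The documents do not support a conclusion that efficacy will be overstated, or by how much. They support a small correction to a stated eligibility rule, worth making because an uncontrolled comparison with baseline depends on a clean baseline.

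**What to change.** Reword exclusion 2 to: *surgical debridement of the target ulcer within 2 weeks before screening or within 2 weeks before V1*. This covers 14 of the last 14 pre-baseline days for every interval from 7 to 35 days.

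Where a debridement takes place after screening, defer V1 inside the 35-day window. That is possible for a debridement up to day 35 − 14 = 21 after screening; beyond that, the single re-screen in section 6.4 is available.

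A line in section 7.2.3 stating that debridement of the target ulcer is not permitted from screening to end of treatment unless clinically necessary, with any procedure dated in the CRF, would make Appendix 6 and section 7.2.1 explicit. It is a clarification and optional. Handling of readings after such a procedure belongs in the separate SAP announced in section 10.3, which is not part of the text available, so no omission is claimed there.

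The cost is one rewording and no new assessment. The downside is a few deferred V1 visits or extra screen failures in a rare disease. The main analysis is unchanged.
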